5.2.1.1 Protocol Changes Occurring During the Study (text added 7/30/2025)

Our original protocol specified that after conducting the RCT (Arm A vs. Arm B), we would conduct a non-randomized clinic-level demonstration project (Arm C) with the App videos shown in clinic waiting rooms. In a protocol deviation, the first 55 participants enrolled in Arms A and B received counseling on HIV TasP/U=U from one of our enumerators during the recruitment phase and coaching on the post-test knowledge questions, regardless of study arm. This data collection error means that both intervention and control participants (Arms A and B) would have received some exposure to HIV TasP/U=U content, attenuating any impact of the intervention. It also means that our analyses of the post-test knowledge and attitudes questions must omit these 55 participants. After recognizing this error, study staff were retrained and recruitment was separated into wave 1 (n=55) and wave 2 (n=80). Following the above protocol deviation, to improve power for our primary comparison, Arm C was dropped and the planned (n=45) participants were distributed to intervention (Arm B) and control (Arm A). Our main analyses include all 135 participants in Arms A and B; in sensitivity analyses we restrict the data to Wave 2 when there was no contamination of the control group.

Our original protocol specified a six-month follow-up survey that would assess changes in patient knowledge, attitudes, and mental health over time. Due to COVID-19 related delays, we were unable to conduct the six-month follow-up survey; hence, we report only on immediate post-test knowledge and attitudes and on clinical outcomes through 10 months, extracted from patient charts. All pre-specified outcomes relying on six-month follow-up surveys were not collected and are not reported on.

Our original protocol specified "VL<50 copies/ml at 6-10 months" as the primary outcome. During the study, a change in national guidelines shifted the timing of the first VL from 6 months to 3 months after ART initiation, leading us to expand our window of observation to 3-10 months. For our primary outcome, we raised the threshold for viral suppression from VL<50 to VL<200 copies/ml, because many patients do not reach VL<50 within 3 months even if they adhere to ART and to be consistent with WHO quidelines specifying <200 copies/ml as indicating zero transmission risk. We additionally report on <50 and <1000 VL thresholds.

Our original protocol specified several clinic visit adherence and retention measures that could not be estimated due to unforeseen limitations. Due to missing dates of next appointments in patient charts and variability in 1-month and 2-month prescribing, we were unable to compute "days late for next appointment" or "days without medication", concepts that underpinned two of our three pre-specified retention measures. In lieu of these measures, we defined new, simplified measures to capture longer-run retention concepts. These measures – any ART refills after 30 days; any ART refills during months 1-2, ...months 3-4, and ...months 5-6 – are robust to 1- and 2-month prescribing, and do not rely on accurate recording of future appointment dates.

These changes are indicated in the relevant places below in this protocol and are reflected in the current record at ClinicalTrials.gov (NCT04504357).

5.2.2. Study population and recruitment.

The study population will include adult men and women (18 years and older) receiving routine HIV counseling services at three public sector clinics in Gauteng, South Africa during the study period. Under current standard of care, HIV counseling is provided at two points in time: after an HIV diagnosis (post-test counseling) and after an elevated viral load (adherence counseling). The same counselors provide both services and the study will recruit from both populations, with at least 1/3 from each group. After their visit to the HIV counselor, patients will be referred to study staff for recruitment into the study. Study staff will explain the study, assure the patient that participation is voluntary, and obtain written consent if the patient wishes to enroll. Across the two study phases, we anticipate recruiting a total of n=135 adult men and women receiving HIV counseling services at three public sector clinics in Gauteng, South Africa. (This sample size is feasible – in a prior study we enrolled 600 newly diagnosed PLWH at four clinics in six months.)

Participants who enroll in the study will participate in surveys at enrolment and at 6-months follow-up. The baseline session, including consent (5 min), intake survey (10 min), intervention (if Arm B) (15min), and immediate post-test survey (25 min), is expected to take 45-60 minutes.

Inclusion / Exclusion: All individuals who receive HIV counseling services, are over 18 years, do not have acute care issues, and are able to consent will be offered enrolment in the study. Patients with acute medical needs who are referred for additional care will not be eligible, so as not to interrupt their care. Patients under 18 years are not eligible. Finally, patients who are not able to consent or who do not consent to participate (including linkage to clinical records) will not be included.

Facility inclusion criteria will be:

- Situated Gauteng province
- Follows national guidelines for viral load monitoring
- HIV positive patient burden≥ 30 per month

Participant inclusion criteria will be:

- Adult patients (>18 years)
- Not pregnant
- (Aim 1) Enrolled in HIV care at study site
- (Aim 2) Received HIV post-test counselling or adherence counselling

Participant exclusion criteria will be:

- Indicates they do not intend to receive HIV care at the study site (Implementation note: this was operationalized as the absence of a clinical chart at the clinic.)
- Requires acute medical care that would be hindered by participation in the study
- Determined by clinical staff not to be physically or emotionally able to initiate ART

- Is currently pregnant
- Does not speak one of the primary study languages: English, Zulu, Sotho, Xhosa
- Is not able to consent (e.g. intoxicated or of limited mental capacity)
- Does not consent to participate in the study, including linkage to clinical records for follow-up of the primary behavioral outcome (ART uptake and adherence over the first 6 months)

5.2.3. Intervention.

The U=U video intervention will be developed in Aim 1. The intervention will be piloted via three treatment modalities: (T1) controlled exposure, using the tablet-based app in the context of a survey; (T2) clinical exposure, in which patients will see the video in the clinic waiting room and will be exposed to the app during HIV counseling; and (T3) text message exposure, with monthly interactive messages.

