5.2.3.1 Intervention assignment, period 1 (two study arms, n=45/arm)

Arm A vs. Arm B. During the first period of recruitment, patients completing HIV post-test or adherence counseling will be referred to study staff for recruitment (Fig 7). Patients will complete a brief intake survey. They will then be randomized 1:1 at the individual level to "no exposure" (Arm A, n=45) vs. "controlled exposure to the tablet-based video intervention" (Arm B, n=45). Arm B will then receive the intervention on tablet, delivered in the study interview setting. Respondents in Arms A and B will then complete additional questions, constituting the immediate post-test survey. Comparisons of outcomes in Arm A and Arm B will enable rigorous inferences on the effect of "controlled exposure" due to randomization.

5.2.3.2 Intervention assignment, period 2 (third study arm, n-45):

Arm C "clinical exposure". We will conduct a demonstration project to assess the feasibility and acceptability of delivering the U=U video intervention in real world clinical settings, rather than in a controlled study context. After period one enrolment has been completed at the three clinics, the intervention will be integrated into routine counseling procedures at each clinic. In collaboration with clinic leadership, HIV counselors will be trained to use the tablet-based U=U intervention to enhance TasP literacy as part of routine counseling and will be provided a tablet for the duration of the pilot. Additionally, the full video intervention will be shown on TVs in the clinic waiting rooms (on repeat, in rotation with other material). All patients receiving counseling at the study clinics after a specified implementation date will be considered "exposed" to the intervention. Patients completing counseling during this period will be referred to study staff for recruitment. Patients who provide consent (Arm C, n=45) will participate in the intake and immediate post test surveys (Fig 7). Comparisons of Arm A and Arm C will enable inferences on the effect of "clinical exposure" to the intervention in a non-randomized pre/post design, comparing patients receiving counseling before and after the intervention at the same facility.

Implementation note: Arm C participants were reallocated to Arms A and B.

5.2.3.4 Text-message reinforcement.

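### Section 5.2.6 was not updated for the wave 1 contamination: the pooled chart-outcome contrast keeps its 'no exposure' label and has no wave term (minor)

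*Combined protocol and SAP*

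**What the plan says.** Section 5.2.1.1 reports that an enumerator counselled the first 55 participants on U=U whatever their arm. It gives the consequence: "both intervention and control participants (Arms A and B) would have received some exposure to HIV TasP/U=U content, attenuating any impact of the intervention". The section removes these 55 from the post-test knowledge and attitude analyses. For everything else it says: "Our main analyses include all 135 participants in Arms A and B; in sensitivity analyses we restrict the data to Wave 2", and describes Wave 2 as the period "in sensitivity analyses we restrict the data to Wave 2 when there was no contamination of the control group".

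Arm C was then dropped and "the planned (n=45) participants were distributed to intervention (Arm B) and control (Arm A"). The note closing 5.2.3.2 says only: "Implementation note: Arm C participants were reallocated to Arms A and B". Section 5.2.3.1 states the allocation for the original two arms ("They will then be randomized 1:1 at the individual level to 'no exposure' (Arm A, n=45"). No ratio is restated for the 45 added places.

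Section 5.2.1.1 also reports a calendar change: "During the study, a change in national guidelines shifted the timing of the first VL from 6 months to 3 months after ART initiation". It ends with the assurance that "These changes are indicated in the relevant places below in this protocol". Implementation notes do appear in 5.2.2, 5.2.3.2, 5.2.3.4, 5.2.4 and 5.2.5.4.

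Section 5.2.6 has no such note. It compares Arm A, labelled 'no exposure', with Arm B, labelled 'controlled exposure', by intention to treat, and adjusts for clinic and counselling type. It mentions neither wave, nor the contamination, nor the Wave 2 analysis, and it still lists comparisons that use Arm C and the six-month survey.

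**The concern.** The 55 are left out of the post-test outcomes, so the pooled analysis of 135 matters for the chart outcomes: VL<200 at 3-10 months, which the note in 5.2.5.4 makes the primary endpoint, and the retention measures. For these, 5.2.6 is where the contrast and the model are defined. Its label fits what Arm A was assigned, but not what the wave 1 controls received. If the pooled result is reported under that label, it will be taken as the effect of the app against no exposure, although by the plan's own account it is an attenuated contrast. A null pooled result could then be read as saying more about the app than it does.

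A second, smaller matter is that the waves are successive recruitment periods, the timing of the first VL changed during the study, and the split of the 45 added places is not given. The model has no term to absorb a difference between waves.

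**Working it through.** **The plan's own figure.** The only power statement (5.2.8) concerns perceived efficacy of treatment as prevention, not the chart outcomes: 20% to 40%, SD 25%, 45 per arm, 97% power. With two-sided alpha 0.05 (assumed; not stated), Φ(20/(25·√(2/45)) − 1.96) = Φ(1.835) = 0.967, so it reproduces. For the chart outcomes there is no figure to reproduce; 5.2.8 says the pilot is not powered for behaviours.

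**Inputs from 5.2.1.1.** Wave 1 n = 55, wave 2 n = 80, total 135. The contaminated share is 55/135 = 40.7%.

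**Assumptions, none in the documents.** Equal allocation within each wave; outcome SD 0.5; an uncontaminated effect of 10 or 20 percentage points; wave 1 keeps a fraction f of that effect, with f between 0 and 1.

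**Attenuation.** Pooled effect ÷ uncontaminated effect = (80 + 55f)/135:
- f = 0: 80/135 = 59%
- f = 0.5: 107.5/135 = 80%
- f = 1: 100%

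The documents give some reason to doubt f near 0. Arm B also had the app on the phone and an information sheet (5.2.3.4), and 5.1.3 expects information alone not to be enough.

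**Precision.** SE = 2 × 0.5/√n. For n = 135 it is 8.61 points (95% half-width 16.9). For n = 80 it is 11.18 points (half-width 21.9).

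**Shortfall and coverage.** Shortfall b = effect × (1 − ratio). Coverage of the uncontaminated effect by the pooled 95% interval ≈ Φ(1.96 − b/8.61) − Φ(−1.96 − b/8.61).

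| Effect | f | Shortfall | Coverage |
|---|---|---|---|
| 10 | 0 | 4.1 | 92% |
| 10 | 0.5 | 2.0 | 94% |
| 20 | 0 | 8.1 | 84% |
| 20 | 0.5 | 4.1 | 92% |

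At f = 1 the shortfall is zero. Every shortfall is inside the pooled half-width; only the extreme corner departs clearly from 95%.

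**Should the pooled set stay the main one?** Its root mean squared error is below that of Wave 2 while b < √(11.18² − 8.61²) = 7.14 points. That means an effect below 7.14/0.407 = 17.5 points at f = 0, or 35.0 points at f = 0.5. This supports keeping all 135.

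**What a wave term does.** Without it, the estimate moves by (outcome shift between waves) × (wave 1 share in A minus that in B). Assume wave 1 was 27/28, the other 35 of the first 90 were 18/17, and the 45 added places split as shown:
- 22/23: 27/67 − 28/68 = −0.009; a shift of 10 or 20 points moves the estimate by 0.1 or 0.2 points.
- 15/30: 27/60 − 28/75 = 0.077; 0.8 or 1.5 points.
- 10/35: 27/55 − 28/80 = 0.141; 1.4 or 2.8 points.

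The term removes this movement at almost no cost: in simulation at an equal split the standard error was 0.084 with or without it. It does not undo attenuation. At 20 points and f = 0 the mean pooled estimate was about 0.12 (80/135 × 0.20 = 0.119) with or without the term.

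**The case against.** The strongest reply is that 5.2.1.1 is the revised plan and already covers this. It discloses the counselling, gives the direction of bias, fixes the main set and plans a Wave 2 analysis that is not limited to particular outcomes; notes in later sections refer back to it. The label in 5.2.6 names the assigned condition, which is normal under intention to treat. All of that stands. There is no concealment, and a bare cross-reference in 5.2.6 would be an editorial matter.

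It is also fair that the sizes rest on assumed effects and an unknown f, that the f = 0 rows are the extreme, and that the timing of the VL guideline change relative to the waves is not given. A real calendar effect on the contrast is therefore conjecture. With 1:1 allocation in each wave, leaving wave out does not bias the comparison.

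A reader might infer more: that the pooled test is invalid, that Wave 2 should replace it, or that the missing wave term confounds the trial. The documents support none of these. Under no effect of assignment, exposure common to both arms creates no difference, so the test holds. The error comparison favours the pooled set over much of the plausible range. Nothing in the text indicates unequal allocation.

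Two things remain. No section says which estimate may carry a statement about the app against no exposure, or whether wave enters the model.

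**Conclusion.** The point holds as a minor one. Section 5.2.6 was not brought into line with 5.2.1.1 for VL<200 and retention. The pooled estimate is 59% to 100% of the uncontaminated effect, depending on an f that the documents do not allow one to know. For assumed effects of 10 to 20 points the shortfall is 0 to 8.1 points, inside a 16.9-point half-width. The consequence is confined to how the chart results are described.

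The expected gain from a wave term is small: 0 to about 3 points under the splits and shifts assumed above, and none if allocation was 1:1 in each wave. The case for it is that it costs almost nothing while the split of the 45 places is unstated.

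**What to change.** Add a dated implementation note to 5.2.6 for the VL and retention outcomes.

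1. Keep all 135 as the main intention-to-treat analysis. Describe it as the effect of assignment to the app when part of the control group had U=U counselling. Show the already planned Wave 2 estimate beside it, and rest any statement about the app against no exposure on Wave 2, labelled as specified after the deviation and less precise.
2. Add wave as a covariate next to clinic and counselling type, labelled as added after the deviation. Check the clinic-by-wave table first: if enrolment moved clinic by clinic, the two may overlap. Say that the term guards against unequal allocation or outcome shifts between waves and does not correct attenuation.

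The cost is one note, one covariate and the placing of a planned estimate; no new data. The drawback is that statements resting on Wave 2 use about 40 per arm, with a half-width near 21.9 points against 16.9 (SD 0.5 assumed).

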	Psy	rchological distress	20
	7.4.	Potential benefits of the proposed research to human subjects and others	
	7.5.	Participant cost and payments	21
	7.6.	Importance of the knowledge to be gained	21
8.	Dat	ta and Safety Monitoring Plan	22
9.	Ref	ferences:	23

3. Summary

The near-elimination of HIV transmission with antiretroviral therapy (ART) has provided the world with a clear path to end the HIV epidemic through the mass provision of ART at diagnosis, i.e. test-and-treat. Despite the substantial prevention benefits of ART, we found minimal knowledge of treatment-as-prevention (TasP) in two population-based surveys we recently conducted in South Africa. Indeed, current public health messaging and clinical HIV counselling in South Africa do not emphasize the prevention benefits of ART. In 2016, U=U Campaign was launched to disseminate the scientific evidence that people with HIV cannot transmit the virus if their viral load is undetectable. U=U has been endorsed by NIH and by organizations in nearly 100 countries. Anecdotal evidence suggests providing information on U=U may reduce stigma and improve the wellbeing of PLWH, and may lead to increased ART uptake and adherence by appealing to the desire of PLWH to avoid transmission to others. Although the science on U=U is clear, there is currently a critical evidence gap on (a) how best to integrate information on U=U into HIV counselling services, and (b) what impact U=U messaging has on the wellbeing of PLWH and treatment-seeking behaviours.

We propose a formative research study (R34) to develop an app-based educational video intervention that will provide information on U=U that is locally-appropriate and can be integrated into routine HIV counselling. We will pilot the intervention in a clinical trial of patients receiving HIV post-test and adherence counselling services, to determine feasibility and acceptability, impact on U=U knowledge and attitudes, impact on stigma and psychological wellbeing, and preliminary evidence for ART uptake, adherence and retention, and viral suppression (primary outcome).

The study builds on a longstanding collaboration between Boston University and the Health Economics and Epidemiology

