The primary goals of the pilot trial are to establish: (a) feasibility of the intervention and data collection methods; (b) acceptability of the intervention, and different video modules and delivery modalities; (c) effects on knowledge about the efficacy of TasP; (d) effects on attitudes towards ART as a prevention strategy (prevention motivation) and treatment strategy (treatment motivation); and (e) preliminary impact on ART uptake and adherence through six months, defined as the number of monthly ART medication pick-ups over the first six months after study enrolment, as measured in linked clinical records. Additionally, we seek to assess the extent to which effects are moderated by patient characteristics including: gender, age, relationship status, post-test vs. adherence counseling, and altruistic preferences.

5.2.5.1 Intake and immediate post-test survey.

The 10-min intake survey will collect basic information on patient demographics and potential moderators. The 25min post-test survey will include the following domains (described in Aim 1): acceptability of the intervention (Arm B, C), beliefs about the health benefits of ART, beliefs about HIV transmission with / without ART, attitudes towards ART as a prevention strategy, HIV prevention altruism, internalized stigma, mental health, partnership status and towards disclosure, self-efficacy to take ART, barriers to adherence, and self-reported adherence and sexual risk behaviors.

5.2.5.2 Six-month follow-up survey.

The six-month follow-up survey will be conducted at the first scheduled clinic visit occurring after six months since enrolment. Once six months have elapsed, all participants will be contacted with a reminder of their next appointment at the clinic and with a reminder that the follow-up survey will be conducted at that visit. Patients will be given the option of participating in the follow-up survey on another date if more convenient, or by phone. All participants will be compensated for their time participating in the follow-up survey. We will attempt at least three contacts in order to retain respondents for the follow-up interview. The six-month follow-up survey will cover the same domains as the immediate post-test survey.

5.2.5.3. Exit interviews (n=30).

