Acceptability will be assessed at immediate post-test with respect to "ease of use" and "usefulness" for intervention study arms (B and C). The intervention will be determined "acceptable" in different subgroups (by moderating variables) if average Likert scores are 3 (out of 4) or higher. We will also assess acceptability, clarity, and salience of specific video modules through embedded questions and rankings in the tablet-based intervention and assessing which were watched again. Other study endpoints will be knowledge and attitudes related to TasP, internalized stigma and mental health, and HIV prevention altruism at immediate post-test and 6 months, and ART uptake and adherence and viral suppression assessed in clinical records. Effects on these endpoints will be assessed through comparisons of study arms. We will conduct separate analyses comparing Arm A ("no exposure") vs Arm B (randomized "controlled exposure"), comparing Arm A ("no exposure") vs Arm C (non-randomized "clinical exposure"), and comparing randomized monthly "text messages" vs. "no text messages" in Arms B and C. For each analysis, treatment arms will be compared across pre-treatment characteristics to assess balance. To evaluate impact, we will compare means for all outcomes across treatment arms using simple linear regression with robust standard errors, adjusting for clinic and type of counselling (stratifying variables). For binary outcomes, we will use logistic regression and estimate marginal effects (risk differences). As a sensitivity analysis, we will adjust for pretreatment characteristics on the intake survey that are substantially imbalanced (p<0.1) and which are thought to be correlated with ART adherence. The trial will be analyzed on an intention-to-treat basis. Every effort will be made to follow up patients for the six-month follow-up survey. Missingness, if >10%, will be addressed via the inverse probability of censoring weights (IPCW). In addition to the "main effects" analyses described, we will assess interactions by theory-driven moderating variables e.g.: counselling type, baseline relationship status, and general altruism.

5.2.7. Sex as a biological variable.

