The study population for this study will be patients who receiving HIV counseling as part of standard of care. These patients include those who have been newly diagnosed with HIV as well as patients who are receiving adherence counseling. Though unlikely, it is possible that information presented on U=U may cause some emotional distress for some potential subjects. The intervention will be implemented in coordination with HIV counselors at public sector

clinics. These counselors are trained to identify and support patients in emotional distress. Patients who counselors identify as being in emotional distress will not be referred to the study. Further, study participants who experience emotional distress during the survey will be referred to the HIV counselors on site for support.

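### Section 5.2.1.1 limits survey reporting to post-test knowledge and attitudes, which leaves out the planned post-test stigma and mental health endpoints for a reason that does not apply to them

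*Combined protocol and SAP*

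**What the plan says.** Section 5.2.1.1 records that "we were unable to conduct the six-month follow-up survey" because of COVID-19 delays, and concludes that "we report only on immediate post-test knowledge and attitudes and on clinical outcomes through 10 months". It then adds: "All pre-specified outcomes relying on six-month follow-up surveys were not collected and are not reported on".

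Other sections plan more than knowledge and attitudes at the enrolment visit. Section 5.2.5.1 lists among the post-test survey domains "HIV prevention altruism, internalized stigma, mental health, partnership status". Section 5.2.6 names as endpoints, to be compared between arms, "knowledge and attitudes related to TasP, internalized stigma and mental health, and HIV prevention altruism at immediate post-test and 6 months". The Aim 2 text in section 4.3 likewise places internalized stigma and mental health in the surveys at enrolment, post-test and six months. The Summary (section 3) gives "impact on stigma and psychological wellbeing" as one of the things the pilot will determine.

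On risk, section 7.2 says that "it is possible that information presented on U=U may cause some emotional distress for some potential subjects". Sections 7.2 and 7.3 deal with this through counsellor screening before referral to the study and through on-site referral.

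**The concern.** Losing the six-month survey removes the later time point for stigma and mental health. It does not remove the earlier one, which belongs to a questionnaire completed at the enrolment visit. The sentence in section 5.2.1.1 nevertheless confines survey reporting to knowledge and attitudes.

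Two things are at stake. First, a stated pilot objective would go unanswered. Section 4.1.6 presents reduced stigma and better mental health as a main reason for spreading U=U information. If planned endpoints disappear in text dated 7/30/2025 without a reason that fits them, the report is open to a concern about selective reporting. Second, with the six-month survey gone, post-test mental health is the only planned quantitative comparison between arms that bears on distress, although the protocol does not assign it to that risk.

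**Working it through.** **Setting the sections side by side**

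1. *What the reason covers.* Section 5.2.1.1 gives one reason, the missing six-month survey, and declares uncollected only the outcomes that rely on it. The note in section 5.2.4 drops that survey and Arm C, nothing else.
2. *Whether stigma and mental health fall under it.* Sections 5.2.5.1 and 5.2.6 place both at the immediate post-test as well as at six months. Only the six-month half is lost.
3. *Whether they count as attitudes.* Section 5.2.6 lists them separately from knowledge and attitudes. In section 5.2.1.1, the sentence describing the original six-month survey names knowledge, attitudes and mental health as three items, and the reporting sentence keeps two.
4. *Whether they are removed elsewhere.* Section 5.2.1.1 ends by saying that the changes are marked where they apply. Sections 5.2.5.1 and 5.2.6 carry no note removing these endpoints.
5. *What else the sentence leaves out.* Read literally, also post-test HIV prevention altruism and acceptability, both planned in section 5.2.6.
6. *Other routes for detecting distress.* Screening and referral (sections 7.2 and 7.3) deal with individual cases. The exit interviews (section 5.2.5.3) ask about challenges caused by the intervention, but they cover Arms B and C only, were timed after the six-month follow-up, and carry no note on whether they took place. None of these gives a scored comparison between arms.

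**What a post-test comparison could detect**

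The plan's one power figure, in section 5.2.8, is for knowledge: 20% against 40%, SD 25%, 45 per arm, 97% power. Alpha is not stated, so two-sided 0.05 is assumed.

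- Standardized difference: (40 − 20)/25 = 0.80.
- Standard error in SD units: √(1/45 + 1/45) = 0.2108.
- Power: Φ(0.80/0.2108 − 1.960) = Φ(1.835) = 0.967, which reproduces the plan's figure.

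On the same basis, the difference detectable with 80% power is (1.960 + 0.842) × √(1/n₁ + 1/n₂) in SD units. Section 5.2.1.1 gives Wave 1 n=55 and Wave 2 n=80, in total 135. The arm splits are not stated, so near-equal arms are assumed.

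| Data | Assumed split | √(1/n₁ + 1/n₂) | Detectable difference |
|---|---|---|---|
| Wave 2 | 40/40 | 0.2236 | 0.63 SD |
| All | 67/68 | 0.1721 | 0.48 SD |

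These figures show how cautiously a result should be worded. They do not bear on whether the endpoints are left out.

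**The case against.** The strongest reply is that the sentence is shorthand for a lost time point. Its neighbour limits the uncollected outcomes to those from the six-month survey, no later note withdraws the post-test measures, and the literal reading would also discard acceptability, which section 5.2.5 counts among the primary goals. This stands as a caution: a deliberate drop is not shown. It does not remove the conflict, because a reader still cannot tell whether the endpoints were collected, analysed or abandoned.

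Two stronger readings are tempting, and the documents support neither.

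- A reader might infer that data in hand are being withheld. The survey and analysis sections are written in the future tense, and nothing confirms that these scales were administered in Aim 2. Section 5.1.6 names the Hopkins checklist and the stigma items for pre-testing only.
- A reader might infer that these scales are the trial's instruments for the distress risk. No section gives them that role. Section 5.1.6 introduces them under mechanisms, as expected benefits, and only the Hopkins checklist is described as measuring distress. Where survey items are meant to track harm, sections 7.2 and 7.3 say so, for adherence and sexual behaviour.

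It is also fair to say that stigma and mental health are missing from the primary goals (a) to (e) in section 5.2.5, and that items asking about past experience may move little after a 15-minute intervention. Both points limit what the result could show. Neither is a reason to leave a planned endpoint unreported.

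**Conclusion.** The point holds as a conflict between sections. Followed as written, section 5.2.1.1 leaves two planned post-test endpoints, internalized stigma and mental health, unreported, along with post-test altruism and acceptability. The one reason given does not reach any of them. This should be corrected whether the sentence was deliberate or loose.

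The conclusion rests on the literal wording and on planned, not confirmed, collection. If the data exist, up to 135 participants could contribute, 80 of them from Wave 2. The detectable differences of 0.63 SD and 0.48 SD depend on the assumed near-equal arms and two-sided 0.05. The comparison would answer a stated objective for same-visit effects only. It could not establish that the intervention causes no distress.

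**What to change.** Amend section 5.2.1.1 to state whether each planned immediate post-test endpoint was collected.

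- **If collected:** report all of them, including mental health and internalized stigma, Arm A against Arm B with the section 5.2.6 model (acceptability in Arm B only, as planned). Show both Wave 2 (n=80) and all 135. Section 5.2.1.1 already omits the 55 Wave 1 participants from post-test knowledge and attitudes analyses. Showing Wave 2 for these measures extends that rule, since U=U counselling at recruitment reached both arms. State that the effects are same-visit, that later distress was not measured by survey, and that with this precision a null result is not evidence of no harm.
- **If not collected:** say so, give the reason, and reconcile sections 4.3, 5.2.1.1, 5.2.5.1 and 5.2.6.

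The cost is one extra table or a short amendment. The drawback is that look-back items may respond little within a single visit, so the table may be uninformative and needs careful wording.
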